9.7.2.4 Comparison of the patient/prescriptions of the two observational periods

The comparison of the patients/prescriptions of the two observational periods (assessment period and reference period) based on IMS[®] Disease Analyzer data will consider the following parameters. The comparisons will be performed separately by physician panel and will be stratified by incident and prevalent users:

- Number and percentage of patients with any diagnosis of disease contraindicated for NSAIDs or weak opioids
- Number and percentage of prescriptions with diagnosis associated with acute pain
- Number and percentage of patients with single and repeated flupirtine prescriptions within the defined time period
- Number and percentage of prescriptions with LFT monitoring during flupirtine treatment
- Length of treatment episodes
- Number and percentage of patients with at least one treatment episode longer than 14 days (based on DDD)

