The PRAC initiated a subsequent benefit-risk evaluation and considered that the controlled clinical studies required by the Note for guidance on clinical investigation of medicinal products for treatment of nociceptive pain (CPMP/EWP/612/00, issued 21 November 2002) for long-term treatment of chronic pain are not available for flupirtine-containing medicinal products². Based on the fact of observed liver effects recorded during long-treatment with Flupirtine and on the absence of controlled long-term clinical studies, the PRAC noted that the management of chronic pain is no longer favourable in terms of the benefit-risk balance for flupirtine-containing medicinal products. The PRAC adopted a recommendation on 13 June 2013 under the provisions of article 107i of Directive 2001/83/EC³.

Taking the currently available data into account, the PRAC decided that the benefit-risk balance for flupirtine-containing products is favourable in the treatment of acute pain, subject to implementation of the following risk minimisation measures⁴:

- Limitation of indication to acute pain in adults if treatment with other analgesics (e.g. NSAIDs, weak opioids) is contraindicated.
- Restriction of Flupirtine use to a maximum of two weeks of treatment.
- Contraindication of Flupirtine in patients with pre-existing liver disease or alcohol abuse.
- Contraindication of Flupirtine in patients concomitantly taking other medications which are known to cause Drug Induced Liver Injury (DILI).

- Weekly liver function tests during treatment and discontinuation in the case of abnormal liver function tests or clinical symptoms.

The PRAC imposed a DHPC, which was distributed on 15 July 2013, in order to communicate the outcome of the PRAC/EMA decision to healthcare professionals⁵. The SmPCs for flupirtine-containing medicinal products have been revised accordingly by Lupin in February 2014 and MAHS marketing flupirtine-containing medicinal products in September/October 2013⁶. The educational material was distributed in February 2015.

Patients and prescribers have been provided with joint educational material according to the PRAC request, prepared jointly by all German MAHs. The educational material, the DUS and a PASS protocol are parts of the RMP.

As of 5 September 2013, the European Commission implemented the decision (C(2013) 5788 final) with the majority opinion of the CMD(h) addressed to all member states based on the PRAC's recommendation⁷.

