Additionally the PRAC requested that the MAHs should submit a risk management plan (RMP) within 3 months after the EC decision. The protocols of two studies - a drug utilization study (DUS) and a PASS should be submitted as part of the RMP.

Hormosan Pharma GmbH launched Flupirtinmaleat-Hormosan 100 mg Hartkapseln in Germany on 31 July 2012, but the marketing of the product was stopped in January 2013. This decision was taken because of commercial and not for safety reasons. Any other MAs held by Lupin Group of companies within EU have not been launched yet. Therefore an extension of deadline for submitting the RMP (including the outline of DUS, PASS and educational material) was received by the Reference Member State (RMS) authority BfArM on 29 November 2013 as the products are currently not marketed.

This protocol covers a design for a DUS based on the information captured in longitudinal patient-level databases and has been designed to fulfill the conditions of the authority.

8. Research question and objectives

The Flupirtine DUS aims to characterise prescribing practices of flupirtine-medicinal products during routine clinical use and to assess the main reasons for prescription by representative groups of prescribers.

The analysis will display by specialty and by prevalent/incident status:

- Number of prescribing physicians
- Region of office (East/West Germany)
- Number of overall patients in the office
- Number of patients with at least one flupirtine containing product

- Patient characteristics: age, gender, insurance status, indication for Flupirtine prescription
- Flupirtine exposure:
 - Number of Flupirtine prescriptions per patient during the 12-month observation period
 - Recommended daily Flupirtine dose (by physicians)
 - Recommended Flupirtine treatment duration (by physicians)
 - Prescription length
 - Indications related to the Flupirtine prescription
 - Co diagnosis within analysis period
 - Concomitant prescription of drugs grouped by relevant ATC classes (Annex 3- ii)
- Administered long-term medications (>14 days) leading to contraindication use of Flupirtine
- Contraindications for use of NSAIDs or weak opioids
- Treatment patterns if available
- Liverfunctions test performed within 1 week after Flupirtine exposure start

9. Research methods

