9.2. Setting

The study will be conducted in the outpatient setting in Germany.

Study population

All patients with a record of Flupirtine prescription during the defined 12-month periods (patient selection window) will be identified from selected database.

The study will include both single users and recurrent users of flupirtine-containing medicinal products.

The study will include two cohorts of patients:

- patients initiated on flupirtine treatment after the review of SmPC in Germany
- patients treated with flupirtine before the review of SmPC in Germany

The two cohorts will include:

- Incident user: patients who had one or more flupirtine prescriptions during the one-year observational period, but no flupirtine prescription for at least 12 months prior to the first flupirtine prescription during the observational period
- Prevalent user: patients who had one or more flupirtine prescriptions during the one-year observational period and at least one flupirtine prescription during the 12 months prior to the first flupirtine prescription during the observational period

Inclusion criteria:

Eligible patients must have at least one prescription of Flupirtine (exposure) during the defined 12-month observational period.

Exclusion criteria:

Exclusion criteria will not be applied.

Study period

The selection of patients from the IMS[®] Disease Analyzer will be carried out in two defined 12-month periods from January 1, 2012 to December 31, 2012 and January 1, 2014 to December 31, 2014, respectively (patient selection window). The date of the first prescription fill in each period will be defined as the exposure start date.

Pre-exposure period:

In order to obtain information about medical history before Flupirtine exposure start, a time period of at least 12 months prior to the individual Flupirtine exposure start date will be analysed for each patient for whom these data are available.

Follow-up:

A follow-up period of one to six months after the exposure start date will be monitored for all patients, and till the end of analysis period for whom these data are available.

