9.7 Data analysis

9.7.1 General remarks

Data from specialist panels will not be combined. The data will be analysed separately by panel (PCP and orthopaedist panel) and for the period before and after SmPC review.

All analyses will be stratified by incident and prevalent users.

Study tables will reference the data source used for each set of results. The data will be presented graphically where useful.

The statistical unit will be the patient (for information such as demographical and clinical characteristics, medical history, contraindications) and the Flupirtine prescription (for information such as indication, number of prescriptions, recommended treatment duration, concomitant drug prescriptions).

The statistical analysis will be done descriptively. Missing values will be reported as missing and no imputation will be conducted. Descriptive tables will be compiled for all variables. Continuous variables will be presented with counts, means, medians, standard deviations, and minimum and maximum values. Categorical variables will be presented in frequency tables. Rates and 95% confidence intervals will be provided when relevant.

Data will be analysed using the statistical software SAS (SAS Institute Inc., Cary, USA) with version 9.3 or above.

All results will be presented in tables. In addition, parameters addressing the primary objectives and eligible for a comparison of time periods (assessment period and reference period) with respect to the effect of risk minimisation measures (for example flupirtine treatment duration) will be presented graphically e.g. by displaying plots or bar charts.

The following section will describe the analyses and definitions used for the DA (**IMS[®] Disease Analyzer**) database.

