9.7.2.1 Patient characteristics of Flupirtine treated patients

The patient characteristics (age, gender, insurance private or SHI) of Flupirtine patients will be described.

- Number of patients within following age groups:
 - < 18 years
 - 18 to 29 years
 - 30 to 39 years
 - 40 to 49 years
 - 50 to 59 years
 - 60 to 69 years
 - 70 years and older

Analyses:

- Number and percentage of Flupirtine patients per age group, gender, insurance status(private or SHI insured)

Indication for flupirtine prescription

In order to describe the indication for flupirtine drugs all diagnoses related to the flupirtine prescriptions will be analysed.

- All diagnoses documented on the prescription of flupirtine will be defined as principal diagnosis.

As not for all prescriptions principal diagnoses will be available, additionally the following approaches will be chosen:

- If there is any disease associated with acute pain (Annex 3-ii) recorded in a time frame of 2 weeks around the date of prescription, this will be defined as associated diagnosis.
- If there is any disease associated with acute pain (Annex 3-ii) recorded in a 12 months history before the date of prescription, this will be defined as co-morbidity.

Principal diagnoses, associated diagnoses and co-morbidities will be analysed separately.

The findings of principal diagnoses will be grouped by diagnosis according to ICD-10 codes (selection of codes see Annex 3) including diseases associated with acute pain and chronic pain.

Analysis:

- Number and percentage of prescriptions, stratified by diagnosis (only principal diagnoses)
- Number and percentage of prescriptions associated with acute pain (principal diagnoses, associated diagnoses and co-morbidities)
- Number and percentage of prescriptions associated with chronic pain (only principal diagnoses)

Contraindication for the use of NSAIDs or weak opioids

The patients' history will be evaluated for medical events referencing to contraindications for NSAIDs or weak opioids (such as myocardial infarction or stroke) for a timeperiod of 12 months prior to first prescription of Flupirtine. Only patients with a history of at least 12 months will be included in this analysis.

Analyses:

- Number and percentage of patients identified as contraindicated of NSAIDs/weak opioid treatment (such as myocardial infarction or stroke)

Long-term medications leading to contraindications for Flupirtin

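### The acute-pain share compared between 2012 and 2014 is counted only per prescription, so a change in repeat prescribing can move it without any change in why patients are treated

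*Protocol*

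**What the plan says.** Section 9.7.1 divides the analyses by statistical unit. Demographics, history and contraindications are counted per patient; the other unit is "the Flupirtine prescription (for information such as indication, number of prescriptions, recommended treatment duration, concomitant drug prescriptions". Section 9.7.2.1 follows this for the indication: "Number and percentage of prescriptions associated with acute pain (principal diagnoses, associated diagnoses and co-morbidities". Its chronic-pain analysis also counts prescriptions and uses principal diagnoses only. Section 9.7.2.4 carries the same unit into the comparison of periods: "Number and percentage of prescriptions with diagnosis associated with acute pain".

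Elsewhere the indication also appears at patient level. Section 8 lists "Patient characteristics: age, gender, insurance status, indication for Flupirtine prescription", and section 9.3 places it under patient characteristics too.

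Three further statements set the context:
- Section 9.2: "The study will include both single users and recurrent users of flupirtine-containing medicinal products".
- Section 7, among the risk minimisation measures: "Restriction of Flupirtine use to a maximum of two weeks of treatment".
- Section 9.7.2.4: the comparisons are made by panel and "will be stratified by incident and prevalent users". The same list includes "Number and percentage of patients with single and repeated flupirtine prescriptions within the defined time period".

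**The concern.** The study is a pre-post comparison, and section 9.7.1 links the comparison of periods to the effect of the risk minimisation measures. Two of those measures are the restriction to acute pain and the two-week maximum. The second should reduce repeat prescribing, and the number of prescriptions per patient sets the weights in the acute-pain percentage. One measure can therefore move the parameter used to judge the other.

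A rise in the percentage could mean that more patients are treated for acute pain, or only that patients with other reasons for treatment received fewer repeats. The parameter cannot separate the two. Stratifying by incident and prevalent status narrows the mixing but does not remove it, because either stratum can hold single and repeat users. The single/repeat row would show that repeats fell; it does not correct the percentage.

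**Working it through.** **Patient numbers (section 9.5, Table 2).** The protocol's own figures reproduce: 11,284 × 0.75 = 8,463 for PCPs, and 1,821 × 0.75 = 1,365.75, stated as 1,365, for orthopaedists. The text rounds these to about 8,400 and 1,300. They are used below only to give a scale for sampling error.

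**Assumed inputs.** The protocol states none of these:
- r: share of patients who are repeat users
- m: mean prescriptions per repeat user in the window
- s: acute-pain share in single users
- q: acute-pain share in repeat users, taken as the same on first and later prescriptions

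**Formulas.**
- Weight of repeat users among prescriptions: w = r·m / [(1 − r) + r·m]
- Share of prescriptions: (1 − w)·s + w·q
- Share of patients: (1 − r)·s + r·q, which does not contain m
- Shift when only m changes: (s − q) × (w before − w after)

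The last line carries the point. The shift is zero if s = q, and its sign follows s − q.

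**Worked case: r = 0.30, m falling from 4 to 2, s = 0.80, q = 0.40.**
- Before: (0.70 × 0.80 + 0.30 × 4 × 0.40) / (0.70 + 1.20) = 1.04 / 1.90 = 54.7%
- After: (0.56 + 0.24) / (0.70 + 0.60) = 0.80 / 1.30 = 61.5%
- Shift: +6.8 points
- Patient level, both periods: 0.56 + 0.12 = 68.0%

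**Same r and m, other shares.**

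| s | q | Shift (points) |
|---|---|---|
| 0.80 | 0.80 | 0.0 |
| 0.80 | 0.70 | +1.7 |
| 0.80 | 0.60 | +3.4 |
| 0.80 | 0.40 | +6.8 |
| 0.60 | 0.80 | −3.4 |

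**Range.** Take r from 0.2 to 0.4, m falling from 3-6 to 2, s = 0.80 and q from 0.40 to 0.70.
- Smallest (r = 0.2, m 3 to 2, q = 0.70): 0.10 × (0.429 − 0.333) = about 1.0 point
- Largest (r = 0.2, m 6 to 2, q = 0.40): 0.40 × (0.600 − 0.333) = 10.7 points

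Two is the fewest prescriptions a repeat user can have, so each case takes the largest possible fall from its starting value. A partial fall gives less: at r = 0.30, s = 0.80, q = 0.40 and m from 6 to 4, the shift is 0.40 × (0.720 − 0.632) = 3.5 points.

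**Scale.** The 95% half-width for a patient-level share of 0.7 is 1.96 × √(0.7 × 0.3 / n). That is 0.98 points at n = 8,400 and 2.49 points at n = 1,300. These are for one period and a whole panel; a difference between periods, or a single incident or prevalent stratum, is less precise.

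**The case against.** The strongest reply is that the prescription is the right unit. The aim is to characterise prescribing and the reasons for it, and the principal diagnosis is the one documented on the prescription. If physicians issue fewer repeats outside acute pain, the make-up of prescribing has really changed. This stands, and it is why the existing parameter should be kept. It does not help a reader who wants to know whether the reasons for treating patients changed.

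A second reply is that the gap between single and repeat users may be small. The acute-pain list in Annex 3-ii includes long-lasting conditions such as arthrosis and spondylosis. The co-morbidity class looks back 12 months from each prescription, so a later prescription can pick up a diagnosis recorded at an earlier one. This also stands: the shift could be near zero or reversed. Its size is unknown in advance.

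A third reply is that the fall in repeats will be visible, through the single/repeat row, episode length and episodes over 14 days. That is so, but none of these re-weights the percentage.

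Some stronger readings are tempting and are not supported:
- **Repeat users dominate the percentage.** They are always over-weighted, but hold a majority of prescriptions only if m > (1 − r)/r, which is 4 at r = 0.20 and 2.33 at r = 0.30. The protocol gives neither quantity.
- **Fewer repeats must shift the percentage.** With equal shares they do not.
- **This is the only compared parameter on the indication.** Section 9.7.2.4 also compares, per patient, the contraindications to NSAIDs or weak opioids, which are the other half of the restricted indication.
- **The protocol contradicts itself on the unit.** Section 8 lists the indication both as a patient characteristic and, under exposure, as related to the prescription. Sections 9.7.1, 9.7.2.1 and 9.7.2.4 agree with one another.

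**Conclusion.** The point holds as a limit on interpretation, not as an error in the chosen unit. The protocol fixes the acute-pain comparison per prescription and plans no patient-level counterpart. A change in repeat prescribing, which the measures are meant to bring about, can therefore be read as a change in the reasons for treatment.

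Under the assumed values the shift is about 1 to 11 points, which can exceed sampling error. It is zero if single and repeat users have equal acute-pain shares and negative if repeat users have the higher share. The direction and size in the real data cannot be stated from the protocol. That the study is descriptive does not remove the problem, since the percentage will be compared between periods with or without a test. The improvement is cheap and worth making.

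**What to change.** Keep the per-prescription percentage in sections 9.7.2.1 and 9.7.2.4. Add to both a row giving the number and percentage of patients whose first flupirtine prescription in the selection window carries an acute-pain diagnosis, using the same diagnosis classes as the row it accompanies. Beside it, give the share of patients whose first prescription has a chronic-pain principal diagnosis. Show both by panel, period and incident/prevalent status. State that a change in the indication is interpreted from the patient-level row, read together with the single/repeat row, and that the per-prescription row describes prescribing volume.

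The cost is one or two extra rows per table. No new data are needed, because section 9.7.2.2 already defines the first prescription in the window as the exposure start. The drawback is that the new row ignores later prescriptions, and for prevalent users the first prescription in the window is not the start of treatment. The retained per-prescription row still covers the later prescriptions.

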Drug utilisation study (DUS) on flupirtine-containing medicinal products.

Retrospective drug utilisation study using patient-level databases to characterise prescribing practices of flupirtine-containing medicinal products during routine clinical use and assess the main reasons for prescription by representative groups of prescribers.

Rationale and background

Due to a rising number of hepatotoxicity reactions during treatment with flupirtine containing products the Co-ordination Group for Mutual Recognition and Decentralised Procedures – Human (CMDh) recommended on 28 June 2013 to restrict the use of oral Flupirtine medicines and suppositories as following:

- treatment of acute (short-term) pain in adults who cannot use other painkillers, such as non-steroidal anti-inflammatory drug (NSAIDs) and weak opioids
- treatment duration limited to not longer than 2 weeks
- after each full week of treatment patients' liver function should be checked
- treatment termination if any signs of liver problems occur
- contraindicated for patients with preexisting liver disease or alcohol abuse problems
- contraindicated for patients taking other medications known to cause liver problems

The recommendations follow a review by the EMA's Pharmacovigilance Risk Assessment Committee (PRAC) which looked into reported liver problems with Flupirtine, ranging from high liver-enzyme levels to liver failure. The PRAC evaluated the available data on liver safety, noting that there were no cases of liver failure or liver transplantation reported in patients who took the medicine for 2 weeks or less. The PRAC also reviewed the available data on the benefits of Flupirtine and concluded that, while there were data from studies in the treatment of acute pain, there were insufficient data to support its use in the treatment of long-term pain.

The CMDh agreed with the PRAC's conclusions and endorsed the PRAC's recommendations on the use of flupirtine-containing medicines. The CMDh position was sent to the European Commission (EC), which endorsed it and adopted a final legally binding decision valid throughout the EU on 5 September 2013.

The reported outcomes were communicated to healthcare professionals by all Germany marketing authorisation holders (MAHs) via a joint Direct Healthcare Professional Communication (DHPC) distributed in July 2013.

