9.7.2.2 Flupirtine exposure

Flupirtine exposure will be defined as one or more prescriptions of Flupirtine. These prescriptions will be identified using the ATC code for Flupirtine or INN. The Flupirtine exposure start date (i.e. the cohort entry date) for each patient will be defined as the date of the first record of Flupirtine prescription during each of the defined twelve-month patient selection window.

Treatment duration

The treatment duration (in days) will be evaluated by using the recommended treatment duration by the physician. If this is not available, the treatment duration cannot be determined exactly as the dose recommendation “as required (pro re nata)” is very often given in the therapy of acute pain. Therefore, the percentage of patients with no information according to recommendation by the physician will be determined.

Prescription length

The prescription length (in days) will be determined as follows:

- For prescriptions with available information on recommended dose per day: from the prescription date plus the expected number of days of drug supply based on the package size and the recommended daily dose
- For all prescriptions without recommendation of dosage: from the prescription date plus the expected number of days of drug supply based on the package size and the DDD(400 mg / day)

The prescription length is therefore not necessarily identical to the treatment duration.

The following parameters will be considered in the analysis for each Flupirtine prescription:

- Date of prescription
- Recommended daily dose by physician
- Recommended treatment duration by physician

Analyses:

- Number and percentage of patients with prescriptions of a flupirtine-containing medicinal product during the 12-month patient selection window
- Treatment duration in days
- Prescription length
- Single use and repeated use

Treatment episodes

A treatment episode will be defined as one or more prescriptions (repeated prescriptions) of flupirtine with gaps between prescription length not more than 7 days. In the case the gap between the prescriptions is longer than 7 days it will be considered as two subsequent treatment episodes. The analysis of treatment episodes will consider prescription length based on DDD, because for all prescriptions this information will be available.

Analyses:

- Number and percentage of episodes
- Min, max, mean, median length of episodes
- Patients within each episode

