9.7.2.3 Monitoring of liver function

For patients where liver function tests after Flupirtine exposure are available (within 1 week after Flupirtine prescription) the following tests will be analyzed in the PCP and orthopaedist panel. Although a feasibility check has shown that laboratory tests are more comprehensively covered in the PCP panel of the database than in the specialist panels, liver function test will also be monitored in the orthopaedist panel in order to ensure comprehensiveness of data.

However, the laboratory tests of the orthopaedist panel will only be included in the analysis in the case sufficient liver function test data are available. A minimum number of 100 laboratory test results per time period will be considered as sufficient.

As Flupirtine treated patients happen to have false positive Bilirubin results, Bilirubin will not be considered the analysis²¹

The proportion of prescriptions with at least one liver function tests within 1 week after prescription date of flupirtine will be estimated.

Liver function tests

- GOT
- GPT
- Gamma-GT
- AP
- Albumin

Analyses:

- Number and percentage of patients with test available
Value of the test

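### The LFT-monitoring percentage counts all prescriptions, including those too short for a test to fall due, so it moves with the mix of prescription lengths

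*Protocol*

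**What the plan says.** Section 9.7.2.3 defines the indicator: "The proportion of prescriptions with at least one liver function tests within 1 week after prescription date of flupirtine will be estimated". Section 9.7.2.4 carries it into the comparison of the two periods as "Number and percentage of prescriptions with LFT monitoring during flupirtine treatment". Neither section sets a minimum supply or duration. Section 9.2 adds no restriction on the population ("Exclusion criteria will not be applied"). The only strata in section 9.7.2.4 are physician panel and incident or prevalent use.

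The rule being evaluated appears twice. The Abstract (Rationale and background) says "after each full week of treatment patients' liver function should be checked". Section 7 lists "Weekly liver function tests during treatment and discontinuation in the case of abnormal liver function tests or clinical symptoms", next to "Restriction of Flupirtine use to a maximum of two weeks of treatment". Section 9.7.1 links the comparison of periods to the effect of the risk minimisation measures.

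Section 9.7.2.2 derives a prescription length from package size and the recommended daily dose or, failing that, the DDD of 400 mg per day. It says the DDD-based length will exist for every prescription. The LFT indicator does not use it.

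**The concern.** On the Abstract's wording, a treatment that ends before a full week has passed never reaches a check. The indicator still keeps such prescriptions in its denominator, and almost all of them can only lower the result. The figure thus mixes two things: how often a due test was done, and how many prescriptions were long enough for one to be due.

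This matters most in the pre-post comparison. The measures introduced between the two years include a limit on duration, so prescription lengths in 2014 may differ from those in 2012. A reader who takes the change in the LFT percentage as a change in adherence could be misled. Stratifying by panel and by incident or prevalent use does not remove this, because neither is a stratum of prescription length.

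**Working it through.** **The plan's own figures.** The protocol gives no LFT rate and no share of short prescriptions. The only figures that can be recomputed are the study sizes in section 9.5, Table 2: 11,284 × 0.75 = 8,463 (PCP) and 1,821 × 0.75 = 1,365.75, printed as 1,365 (orthopaedist). Both agree. The PCP figure is used below only as a scale for precision.

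**What counts as short.** At the DDD in section 9.7.2.2, 7 days need 7 × 400 mg = 2,800 mg, which is 28 units of 100 mg or 7 units of 400 mg. Anything smaller lasts under a week. Annex 3 lists products without pack sizes, so how often this occurs cannot be told.

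**Formula.** Let s be the share of prescriptions with under 7 days of supply, r the testing rate where a test is due, and r0 the testing rate in short prescriptions. Then

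reported % = (1 − s) × r + s × r0,

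and, with r and r0 unchanged, the shift between years is −(s in 2014 − s in 2012) × (r − r0).

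**Scenario 1: no change in testing.** Take r = 20% in both years. All values of s, r and r0 are assumptions. Cells show reported % in 2012 → 2014.

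| s, 2012 → 2014 | r0 = 0% | r0 = 5% | r0 = 10% | r0 = 20% |
|---|---|---|---|---|
| 10% → 20% | 18.0 → 16.0 | 18.5 → 17.0 | 19.0 → 18.0 | 20.0 → 20.0 |
| 10% → 40% | 18.0 → 12.0 | 18.5 → 14.0 | 19.0 → 16.0 | 20.0 → 20.0 |
| 20% → 50% | 16.0 → 10.0 | 17.0 → 12.5 | 18.0 → 15.0 | 20.0 → 20.0 |

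Where r0 is below r, the fall is 1.0 to 6.0 points. Where r0 equals r, there is none. Restricted to prescriptions with a test due, the figure is 20% in both years throughout. The shift scales with r − r0: at r = 50% and r0 = 5%, s going from 10% to 40% gives 45.5% → 32.0%. If s fell instead of rising, the sign would reverse.

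To keep the reported figure level when s goes from 10% to 40%, true testing would have to rise from 20% to 25% (r0 = 10%) or to 30% (r0 = 0).

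**Scenario 2: 2012 testing unrelated to length.** Suppose 5% of all prescriptions were tested in 2012. Suppose that in 2014 testing where due rises to 20% while short prescriptions stay at 5%. At s = 40% in 2014 the reported figure is 0.6 × 20% + 0.4 × 5% = 14%. The true change of 5% → 20% is shown as 5% → 14%. This dilution needs no change in the mix.

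**Against sampling error.** With 8,463 independent observations, the 95% half-width is 1.96 × √(0.18 × 0.82 / 8,463) = 0.8 points at 18% and, likewise, 0.7 points at 12%. For the difference it is √(0.82² + 0.69²) ≈ 1.1 points. A 1-point artefact would be lost in the noise, whereas one of 3 to 6 points would look like a real change. This is only a scale: 8,463 counts patients rather than prescriptions, and it ignores clustering and the incident/prevalent split.

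**The numerator.** Section 9.7.2.3 counts tests in the first week after the prescription date, section 9.7.2.4 speaks of tests during treatment, and the Abstract places the check after a full week. A test done when due falls at the edge of the section 9.7.2.3 window or outside it.

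**The case against.** A reader might infer that the indicator is biased against 2014 because the better prescribers keep to the duration limit, the lower the LFT percentage goes. The protocol does not support that. The limit is two weeks, not one. A prescriber who cuts supply to 14 days still reaches the first full week, and no listed restriction asks for less than 7 days. Nothing in the protocol shows that such prescriptions are common or became more common. Large artefacts can be produced, such as 27% → 18% with r = 30%, r0 = 0 and s rising from 10% to 40%, but they rest on chosen values and on short prescriptions never being tested. This part of the objection stands: size and direction are open.

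Four further points have some weight.

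- Supply is a poor guide to use. Section 9.9 says as-needed dosing is very common and actual treatment often shorter than the prescription. A supply filter will therefore leave in some patients with no test due. That limits the remedy without justifying the unrestricted denominator.
- Trimming the denominator alone does not yield adherence, because the numerator window may miss a due test. This is right, and the two must be corrected together.
- Eligibility for one descriptive percentage could be settled in the SAP, which is not at hand. However, the protocol itself fixes the unit and the definition, so the plain reading is all prescriptions. An SAP that restricted it would answer the point.
- Episode length is compared next to the LFT percentage, so a shift in length would be visible. A reader would still be unable to separate its effect from a change in testing.

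**Conclusion.** The point holds in a conditional form. As worded, the indicator counts prescriptions for which no test falls due, so it cannot be read as adherence to the monitoring rule. The pre-post comparison is distorted if short prescriptions are tested less often than longer ones and either their share changes or testing improves only where it is due. The result may be a spurious decline, an understated improvement or, if testing does not depend on length, no shift. The 1 to 6 points hold only for r = 20% and the assumed shares. The protocol gives no pack sizes, share of short prescriptions or testing rate to narrow this. It does not establish a bias against 2014. Because the indicator is one of the listed comparison parameters and the correction is cheap, it is worth making even with the size unknown.

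**What to change.** In sections 9.7.2.3 and 9.7.2.4:

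- Keep the prescription as the unit. Report the LFT percentage among prescriptions whose own supply, or supply continued without a gap by a follow-on prescription, reaches at least 7 days. Use one length rule, applied identically to 2012 and 2014, and state which prescription in a continuous run carries the test.
- Report the number of shorter prescriptions separately as no test due, and keep the all-prescription percentage alongside.
- Use one fixed test window per prescription in both years. Reconcile section 9.7.2.3, section 9.7.2.4 and the Abstract so that the numerator can capture a due test.
- State that supply is only a proxy for treatment, given as-needed use (section 9.9).

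The treatment episodes of section 9.7.2.2 should not serve as the denominator. They bridge gaps of up to 7 days, so two short prescriptions could pass as a full week. If any test in an episode counts, longer episodes also have more chances: at an assumed 10% per week, two weeks give 1 − 0.9² = 19% and eight weeks 1 − 0.9⁸ = 57%.

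The cost is a change of wording, a filter on a variable already derived and one extra table row. The price is a smaller denominator and some remaining misclassification.
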